3.2. Efficacy Analysis Set

Efficacy analysis set will be included all patients who received at least 1 dose of Xeljanz® according to the local product document, and are available for an efficacy assessment performed after 6 months of treatment, or based on the last assessment performed at the time of treatment discontinuation if the patient dose not complete 6 months of treatment.

The following cases will be excluded from the efficacy analysis set in the following order:

- Patients who are excluded from the safety analysis set
- Patients without overall assessment as efficacy assessment item

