## 7. RESEARCH METHODS

### 7.1. Study design

This is an open-label, non-comparative, non-interventional, prospective, and multi-center study conducted in Korean health care centers by accredited physicians (ie, investigators). The study population will be adult patients with moderately to severely active RA who have had an inadequate response or intolerance to methotrexate. Xeljanz will be administered according to the “Dosage and Administration” of the approved labeling. There is no visit or activity mandated by this study. The investigator will collect patient data and record the information on each patient’s case report form (CRF).

CCI

Also, investigators collect data on the Xeljanz retrospectively from the subjects who have been administered the Xeljanz according to the local product documents but not participated in this study until 26 June 2022.

Safety is the primary interest of this study, which will be assessed based on adverse events (AEs) that occur during the 6 months from the first dose of Xeljanz. The efficacy endpoints will be the modified Disease Activity Score using 28 joint counts (DAS28) change from baseline, [European League Against Rheumatism](#) (EULAR) response, and American College of Rheumatology 20% improvement criteria (ACR20) response after treatment (see [Section 7.3](#)).

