### 7.3.2. Efficacy variables

Efficacy variables include DAS28, EULAR response, and ACR20 response. The investigator can make an assessment of the overall efficacy – improved, no change, aggravated - based on each test results and clinical judgment.

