#### 7.3.2.1. Efficacy evaluation

Efficacy assessment will be performed by the accredited investigator in the Korean health care center. In the case of RA, The investigator will perform the efficacy assessment at baseline and after 6 months of treatment by any of the commonly used efficacy assessment criteria such

as DAS28 and American College of Rheumatology 20% improvement criteria (ACR20), and record the assessment results in each patient's CRF. If the patient dose not complete 6 months of treatment, relevant data should be collected based on the last assessment performed at the time of treatment discontinuation.

DAS28, a modified version of the original Disease Activity Score (DAS), is a quantitative measure of disease activity used to monitor the treatment of [RA](#). DAS28 is calculated using the following formula that includes the number of tender joints and swollen joints (28 joints maximum).

$$\text{DAS28 (ESR)} = 0.56 \times \sqrt{(\text{TJC 28})} + 0.28 \times \sqrt{(\text{SJC 28})} + 0.014 \times \text{VAS} + 0.70 \times \ln(\text{ESR})$$

[figure not shown]
or,

$$\text{DAS28 (CRP)} = 0.56 \times \sqrt{(\text{TJC 28})} + 0.28 \times \sqrt{(\text{SJC 28})} + 0.014 \times \text{VAS} + 0.36 \times \ln(\text{CRP}+1) + 0.96$$

Of which, CRP=C-reactive protein, ESR=erythrocyte sedimentation rate, SJC28=28 swollen joint count, TJC28=28 tender joint count, VAS=visual analogue scale

The DAS-based EULAR response criteria (see Figure 1) classify individual patients as none, moderate, or good responders, depending on the extent of change and the level of disease activity reached.

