**Figure 1 DAS28-based EULAR response criteria**

An ACR20 response is defined as at least 20% improvement in both the tender joint count and the swollen joint count and at least 20% improvement in 3 of the 5 other disease activity measures (items 3 to 7) listed in [Table 2](#). If ACR20 is assessed in the usual clinical practice, the results should be recorded as “done-achieved” or “done-not achieved”. If ACR20 is not assessed, the investigator records “not done” in the CRF.

In the case of PsA, the number of active joints, including number of tender and swollen joints at 3 months of treatment is measured. DAS28 can be calculated based on the number of active joints, and DAS28 calculation is the same as calculation of RA above.

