### 7.7.2. Efficacy analysis

Efficacy analysis will be performed on an intent-to-treat basis. It will be analyzed for all patients entering this study, who received at least 1 dose of Xeljanz according to the local product document, and are available for an efficacy assessment performed after 6 months of treatment, or based on the last assessment performed at the time of treatment discontinuation if the patient dose not complete 6 months of treatment.

Analysis with effectiveness of treatment based on change from baseline in DAS28, after a treatment EULAR response and after a treatment ACR20 response. Evaluation of overall

assessment including 'Improve', 'Changeless', 'Aggravated' - based on each test results and clinical judgment analysis. As a result of evaluation, 'Without any assessment' remains with not available effectiveness result. 'Improve', 'Changeless', 'Aggravated' remain with available effectiveness. Overall assessment evaluation conclude with 'Improve' that Xeljanz is effective. Overall assessment evaluation conclude with 'Changeless' or 'Aggravated' that Xeljanz is less effective.

CCI

If the patient discontinues prematurely without completing the 6 months treatment, the reason of discontinuation will be analyzed.

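### SAP 3.2 removes patients without the investigator's overall rating from the only visible efficacy set, so any DAS28, EULAR or ACR20 results they have are left out of the analysis

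*SAP*

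**What the plan says.** SAP 3.2 admits treated patients who "are available for an efficacy assessment performed after 6 months of treatment", or who have a last assessment at discontinuation. Protocol 7.7.2 uses the same admission wording and describes the analysis as intent-to-treat. SAP 3.2 then lists exclusions, the second being "Patients without overall assessment as efficacy assessment item".

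SAP 6.5 states that efficacy is analysed on the efficacy analysis set. It lists four analyses: (1) DAS28 change, (2) EULAR response, (3) ACR20 response and (4) the overall assessment split into effective and not effective. No other efficacy set is visible.

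On the endpoints, Protocol 7.1 says "The efficacy endpoints will be the modified Disease Activity Score using 28 joint counts (DAS28) change from baseline", followed by EULAR and ACR20 response. SAP 2.2.1 repeats this. The overall assessment is not in that list; it appears as item 4 of SAP 4.5, where 'Not Done' is one of its entries. Protocol 7.3.2 makes it optional: "The investigator can make an assessment of the overall efficacy". Protocol 7.3.2.1 lets RA efficacy be assessed "by any of the commonly used efficacy assessment criteria such" as DAS28 and ACR20, and gives ACR20 its own CRF entry: "If ACR20 is assessed in the usual clinical practice, the results should be recorded as" done-achieved or done-not achieved.

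**The concern.** Whether a patient's measured result on a named endpoint is analysed depends on whether a different, discretionary field was completed. The exclusion is narrower than the admission sentence just above it: a patient with a six-month DAS28 has an efficacy assessment by any ordinary reading, yet is removed if the overall rating is blank or 'Not Done'. SAP 5.1.1 applies no imputation, so nothing brings that patient back.

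What is at stake is some precision, possible selection if unrated patients respond differently, and a reported denominator that does not count everyone measured. Safety, the primary interest, is not affected.

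**Working it through.** The documents give no count of unrated patients, so there is no plan figure to reproduce. The check has two parts.

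**1. Following one patient through the text.** Take an RA patient with DAS28 at baseline and six months, ACR20 recorded as achieved, and the overall assessment recorded as 'Not Done'.

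- Admission sentence of SAP 3.2: met, since an efficacy assessment at six months exists.
- Exclusion list of SAP 3.2: removed, since the overall assessment is missing.
- SAP 6.5 items 1 to 3: not analysed, since all use the efficacy set.
- SAP 5.1.1: no imputation, so not recovered.
- SAP 6.6 by-indication tables: unclear. These repeat the 6.5 items, but SAP 3.4 defines the sub-groups only as subjects with RA or with PsA and does not say whether they sit inside the efficacy set.

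Such patients could exist. Protocol section 4 plans data collection from 01 May 2015, and the amendment log dates the addition of the overall assessment to Amendment 03, 25 January 2016. A patient treated from the planned start would have reached six months around 01 November 2015, before the item was added. The documents do not show whether enrolment kept to that date or whether the rating was added to those records later, so this is a possible route only.

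**2. Size under assumed shares.** Let m be the share of patients with a measured endpoint but no rating. The values of m are assumptions, with zero also possible. Equal variance in rated and unrated patients is assumed for the standard error.

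- Standard error of mean DAS28 change: factor 1/sqrt(1 − m).
- Bias in that mean: mean(rated) − mean(all measured) = m × [mean(rated) − mean(unrated)]. It is zero if the groups do not differ.
- EULAR or ACR20 proportion: if p is the proportion among rated patients, the proportion among all measured patients lies between (1 − m)p and (1 − m)p + m, a band of width m that needs no assumption about the unrated.

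| m (assumed) | SE factor | Band for p = 60% (example) |
|---|---|---|
| 1% | 1/sqrt(0.99) = 1.005 | 59.4% to 60.4% |
| 5% | 1/sqrt(0.95) = 1.026 | 57% to 62% |
| 10% | 1/sqrt(0.90) = 1.054 | 54% to 64% |
| 20% | 1/sqrt(0.80) = 1.118 | 48% to 68% |

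For the bias, an assumed difference of 0.5 to 1.0 DAS28 units with m of 5% to 20% shifts the mean by 0.05 × 0.5 = 0.025 up to 0.20 × 1.0 = 0.20 units. The direction is unknown.

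**The case against.** The strongest reply is that the affected group may be empty. Protocol 7.7.2 sets three ratings against a fourth category, patients without any assessment, for whom it says the patient "remains with not available effectiveness result". If 'Not Done' in the SAP means the same thing, the exclusion removes only patients with nothing to analyse. The paragraph also opens with "Analysis with effectiveness of treatment based on change from baseline in DAS28", so the SAP rule could be a faithful implementation of the protocol. The rating rests largely on these same measures, so an investigator holding two DAS28 values could normally give one. In addition, Protocol 7.6 sends missing data back to the site as queries, and SAP 5.1.1 promises to evaluate the impact of missing data.

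Part of this stands. The number affected may well be very small or zero, and the protocol line is ambiguous. It does not remove the point. SAP 4.5 makes the overall assessment a specific item separate from DAS28, EULAR and ACR20, and the exclusion is worded by that item. The protocol line does not say that measured DAS28 or ACR20 values are discarded. A recorded 'Not Done' is a valid entry that a missing-data query need not catch, and SAP 5.1.1 names no method. Two limits also stand: redacted text follows in Protocol 7.7.2 and SAP 6.5, and the by-indication tables might, read literally, include unrated patients.

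**Conclusion.** The concern holds on the visible text. Applied as written, SAP 3.2 and 6.5 drop collected results on the endpoints named in the design because an optional item is missing. The size is not known from the documents. With no unrated patients there is no effect; at an assumed 5% the standard error rises by 2.6% and a response proportion is uncertain over a 5-point band; at 20% the figures are 11.8% and 20 points. No bias is shown, and no direction can be claimed. Because efficacy is secondary and the output is mainly descriptive, this should be corrected as a low-cost improvement. Confidence is medium, given the ambiguous protocol line and the redactions.

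**What to change.** Change the SAP only:

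- In 3.2, limit the overall-assessment exclusion to 6.5 item 4. Leave the timing condition in the admission sentence as it is.
- Within the safety set, analyse 6.5 items 1 and 2 in all patients with baseline and final DAS28, and item 3 in all patients with ACR20 recorded as achieved or not achieved.
- In 6.6, state that the same rule applies to the by-indication tables.
- Report N for each endpoint and the number of patients measured but not rated. That count would also show whether the issue had any practical effect.

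The cost is a wording change in 3.2 and one line in 6.6, with no new data. Protocol 7.7 allows the SAP to modify protocol plans and calls for an amendment only for major changes to primary endpoint definitions or their analyses, so none is needed. The effectiveness ratio that the amendment log attributes to a regulatory request keeps its present set. The downside is that denominators differ by endpoint and must be shown; they can already differ, since DAS28 or ACR20 may be missing in rated patients.

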3.3. Special Patient Population

Special patient population will include elderly people (age ≥ 65) or patient with renal or hepatic disorders who have been administered Xeljanz® during the study, respectively.

3.4. Sub-group Analysis set by Indication

The following sub-groups are defined for sub-group analysis of safety and efficacy by indication:

- Sub-group 1: Subjects with RA indication.
- Sub-group 2: Subjects with PsA indication.

3.5. Off-label Evaluation Patients

Off-label evaluation patients will be included patients who have experienced off-label use against Xeljanz® local product document during the study.

4. Study Endpoints

4.1. Demography and Baseline Characteristics

Demography and baseline characteristics include the following.

- Demography characteristic (Age, Sex, Height, Weight)
- Herpes zoster vaccination

Statistical Analysis Plan

- Smoking
- Indication (RA, PsA)
- Duration of the disease
- Severity of disease activity
- Radiologic progression
- Previous treatments (Status (yes/no), previous RA or PsA drugs classified by latest version of Anatomical Therapeutic Chemical (ATC) code as level 1 and level 2)
- Latent tuberculosis
- Renal/hepatic disorder
- Other past/present diseases (Status (yes/no), past/present disease classified by latest version of MedDRA)
- Allergic history

4.2. Administrative Status for Medicinal Products

- Treatment duration
- Daily dose

4.3. Concomitant Treatments

Assessment variable for concomitant treatments of patients will be included the following.

- Concomitant medication status
- Concomitant drugs classified by latest version of ATC code as level 1 and level 2

4.4. Safety Endpoints

The incidence and number with 95% confidence interval for all adverse events/adverse drug reactions investigated within 6 months from initial dosing after at least 1 dose of Xeljanz® during the study.

- Seriousness
- Severity
- Causality assessment
- Action taken
- Outcome

4.5. Efficacy Endpoints

Efficacy variables will be included DAS28, EULAR response, and ACR20 response. Also, overall assessment will be performed as 'Improved', 'No change', 'Aggravated' and 'Not Done' based on the variables, tests and clinical discretion by investigator.

Statistical Analysis Plan

1) DAS28

DAS28, a modified version of the original Disease Activity Score (DAS), is a quantitative measure of disease activity used to monitor the treatment of RA. DAS28 is calculated using the following formula that includes the number of tender joints and swollen joints (28 joints maximum).

$$DAS28(ESR) = 0.56 \times \sqrt{TJC28} + 0.28 \times \sqrt{SJC28} + 0.014 \times VAS + 0.70 \times \ln(ESR)$$

or,

$$DAS28(CRP) = 0.56 \times \sqrt{TJC28} + 0.28 \times \sqrt{SJC28} + 0.014 \times VAS + 0.36 \times \ln(CRP + 1) + 0.96$$

Abbreviations: ESR=erythrocyte sedimentation rate, CRP=C-reactive protein, TJC28=28 tender joint count, SJC28=28 swollen joint count, VAS=visual analogue scale

2) EULAR response

The DAS-based EULAR response criteria classify individual patients as none, moderate, or good responders, depending on the extent of change and the level of disease activity reached (refer to the Figure 1).

[Figure 1] DAS28-based EULAR response criteria

DAS28 at endpoints	Improvement in DAS28 from baseline
≤ 3.2	Good
>3.2 and ≤ 5.1	Moderate
>5.1	None

3) ACR20 response

An ACR20 response is defined as at least 20% improvement in both the tender joint count and the swollen joint count and at least 20% improvement in 3 of the 5 other disease activity measures (item 3 to 7) listed in Table 1. If ACR20 is assessed in the usual clinical practice, the results should be recorded as “done-achieved” or “done-not achieved”. If ACR20 is not assessed, the investigator records “not done” in the CRF.

[Table 1] American College of Rheumatology Preliminary Definition of Improvement in Rheumatoid Arthritis

Disease activity measures:

1. Tender joint count
2. Swollen joint count

Statistical Analysis Plan

3. Patient's assessment of pain
4. Patient's global assessment of disease activity
5. Physician's global assessment of disease activity
6. Patient's assessment of physical function
7. Acute-phase reactant value: ESR or CRP level

Abbreviations: ESR=erythrocyte sedimentation rate, CRP=C-reactive protein

4) Overall assessment

Overall assessment will be performed as 'Improved', 'No change', 'Aggravated' and 'Not Done' based on the variables, tests and clinical discretion by investigator.

5. General Consideration

5.1. Handling of Missing and Incomplete data

5.1.1. Handling of Missing data

If data are missing or if a subject decides to discontinue from the study, there will be no imputation applied. The impact of missing data will be evaluated as appropriate.

5.1.2. Handling of Missing and Incomplete date

Missing or incomplete dates will be handled by following rule:

	Missing	Imputation
Date of treatment stop date	DD	01
	MM/DD	01/01
	YYYY/MM/DD	No imputation

6. Statistical Analyses

6.1. Demography and Baseline Characteristics

Demography and baseline characteristics will be demonstrated by descriptive statistics.

Continuous variables will be summarized by descriptive statistics (n, mean, standard deviation, median, minimum and maximum) and categorical variables will be presented in frequency and percentage (n, %).

- Age will be presented in n, mean, standard deviation, median, minimum and maximum and frequency and percentage of categorized age groups (exact age will be calculated based on birth year and month).
- Sex will be presented in the frequency and percentage.
- Height (cm) and weight (kg) will be presented in the frequency and percentage of

Statistical Analysis Plan

categorized height and weight groups.

- Herpes zoster vaccination status and smoking status will be presented in frequency and percentage.
- Indication (RA, PsA) will be presented in the frequency and percentage.
- Duration of the disease will be presented in n, mean, standard deviation, median, minimum and maximum.
- Severity of disease activity and radiological progression status will be presented in frequency and percentage.
- Previous RA or PsA treatment will be presented in frequency and percentage and specifically, previous RA or PsA drugs classified by latest version of ATC code will be presented in frequency and percentage.
- Status of latent tuberculosis will be presented in frequency and percentage.
- Past/present disease status will be presented in frequency and percentage and past/present disease classified by latest version of MedDRA in detail will be presented in each frequency and percentage.
- Renal/hepatic disorder status and allergic history will be presented in frequency and percentage.

6.2. Administrative Status for Medicinal Product

- Treatment duration and daily dose will be presented by descriptive statistics as n, mean, standard deviation, median, minimum and maximum. If treatment is ongoing, the date of final efficacy evaluation will replace the treatment stop date. But, if the treatment is ongoing after the date of final efficacy evaluation, the date of signature of investigator will replace the treatment stop date.

$$\text{Total treatment duration(day)} = \sum_{First}^{Last} \{(Stop date) - (Start date) + 1\}$$

- Total dose (mg) will be presented by descriptive statistics as n, mean, standard deviation, median, minimum and maximum.

$$\text{Total dose(mg)} = \sum_{First}^{Last} \{(Daily dose)\} \times \{(Stop date) - (Start date) + 1\}$$

- Daily average dose (mg/day) will be presented by descriptive statistics as n, mean, standard deviation, median, minimum and maximum.

$$\text{Daily average dose(mg/day)} = \frac{\text{Total dose}}{\sum_{First}^{Last} \{(Stop date) - (Start date) + 1\}}$$

Statistical Analysis Plan

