#### 5. RATIONALE AND BACKGROUND

Xeljanz® (tofacitinib) is a potent, oral janus kinase inhibitor. Xeljanz was approved by the Ministry of Food and Drug Safety (MFDS) on 02 April 2014 for the treatment of adult patients with moderately to severely active rheumatoid arthritis (RA) who have had an inadequate response or intolerance to methotrexate. It may be used as monotherapy or in combination with methotrexate or other nonbiologic disease-modifying anti-rheumatic drugs (DMARDs).

In addition, MFDS approved new indications for the treatment of adult patients with active psoriatic arthritis (PsA) who have had an inadequate response or intolerance to previous antirheumatic drugs (DMARDs) on 20 Sep 2018. It may be used in combination with methotrexate or other nonbiologic disease-modifying anti-rheumatic drugs (DMARDs). The efficacy of Xeljanz as a monotherapy has not been studied in psoriatic arthritis.

CCI

CCI

Background information on Xeljanz can be obtained from the current version of the local product document (ie, local labelling), which is the single reference safety document (SRSD) for information relating to Xeljanz in this study.

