### 7.2.5. Study procedures

The investigator should enroll all patients to whom Xeljanz is prescribed for the first time according to the local product document and who agree to participate in this study by signing the data privacy statement (used in place of the informed consent form) by continuous registration method. In case of the patients who already have been administered Xeljanz but not participated in this study, study related information from the first administration until the last day of the observation period should be collected retrospectively. Xeljanz tablets will be medicated by the investigator's prescription under usual clinical practice. Pfizer Korea will not provide the medicinal product for this study.

There will be no mandatory visit during the study. The investigators will collect relevant data from the time of initiating administration of Xeljanz until 6 months of treatment. If the patient does not complete 6 months of treatment, relevant data should be collected based on the last assessment performed at the time of treatment discontinuation. The investigator should record the following information on the patient's CRF:

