#### 7.2.5.1. Information of institution

The following will be recorded on the CRF for each patient:

- Name of institution: Enter the code number assigned to each institution.
- Patient number: The investigator will sequentially assign each patient a patient identification number, which will be a 4-digit number. The total number of cases that need to be collected will be allocated to each study site by Pfizer at the time of execution of a contract with each site.
- Completion of the study: If the patient completed 6 months treatment, check "yes". Otherwise, check "no" and choose reason for the discontinuation: AE; lack of efficacy; others.

- Date of CRF completion: Record the date of CRF completion.
- Signature of investigator: Contracted investigator must sign after identifying the CRF.
- Confirmation of data privacy statement: If the patient has signed the data privacy statement to indicate agreement for using his/her personal and medical information, check the box of “yes” on the CRF in case of subjects to be collected data prospectively. If not, check “no” and exclude the case from the study. If the patient has signed the data privacy statement, check the box of “yes” on the CRF in case of subjects to be collected data retrospectively, and if not, check “no” on the CRF and check if it is available for the exempt of the data privacy statement according to the IRB/IEC’s decision

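### SAP 5.1.2 can impute a stop date before the start date, and SAP 6.2 can extend ongoing treatment to the CRF signature date, so some descriptive exposure values can be impossible or unverified

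*SAP*

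**What the plan says.** **Partial dates.** SAP 5.1.2 states "Missing or incomplete dates will be handled by following rule". Its table covers the treatment stop date: missing day becomes 01, missing month and day become 01/01, and a wholly missing date is not imputed. Nothing refers to the start date.

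**Ongoing treatment.** SAP 6.2 first replaces the stop date of ongoing treatment with the date of the final efficacy evaluation. It then adds that "if the treatment is ongoing after the date of final efficacy evaluation, the date of signature of investigator will replace the treatment stop date".

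**Formulas.** SAP 6.2 sums Stop − Start + 1 over records for duration, sums daily dose times those days for total dose, and divides the two for daily average dose. There is no lower or upper limit.

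**What is collected.** Protocol 7.2.5 has investigators "collect relevant data from the time of initiating administration of Xeljanz until 6 months of treatment". For patients already treated, "study related information from the first administration until the last day of the observation period should be collected retrospectively". Protocol 7.2.5.3 asks only for a start date when the drug is still being taken at study completion. Protocol 7.2.5.1 says of the signature only that "Contracted investigator must sign after identifying the CRF"; it sets no time for it. Protocol 7.1 describes retrospective collection from patients who were treated "but not participated in this study until 26 June 2022". Protocol 7.6 sends missing or questionable data to site query.

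**The concern.** The imputation rule moves a stop date to the earliest day it could be, whether or not treatment had begun by then. A treatment that starts and stops in the same month (day missing) or the same year (month and day missing) can then have zero or negative days and milligrams. A zero total duration leaves the average dose undefined. A negative record within a multi-record patient distorts the average without producing an obviously impossible total.

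The signature-date rule has a different weakness. It carries treatment, at the last recorded dose, to an administrative date. Since an ongoing record has a start date only, the data described do not separate treatment that is ongoing from treatment that is ongoing after the final evaluation. Either sentence of 6.2 could be applied to the same patient, and the number affected cannot be told from the documents.

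At stake is the credibility of the exposure tables that accompany the safety results, not the safety results themselves.

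**Working it through.** The plan gives no figure to reproduce. The check applies the SAP's own formulas to dated examples. Six months is taken as 183 days (181 to 184 by calendar).

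**1. Partial stop date, one record.** Start 15 March 2017.
- Stop known as March 2017, imputed 1 March: −14 + 1 = **−13 days**.
- Stop known as 2017, imputed 1 January: −73 + 1 = **−72 days**.
- Start 2 March 2017 with stop March 2017: −1 + 1 = **0 days**, so average dose is 0/0.

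**2. How often, among dates that are still partial.** Take every start date in 2017 and a true duration of L days.
- Day missing: the result is ≤ 0 when start and stop share a month and the start is on day 2 or later. For L ≤ 28 that is 365 − 12L start dates.
- Month and day missing: it is ≤ 0 when both fall in 2017 and the start is after 1 January, which is 365 − L start dates.

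| Missing part | True duration | Start dates giving ≤ 0 | Share |
|---|---|---|---|
| Day | 7 days | 281 of 365 | 77% |
| Day | 14 days | 197 of 365 | 54% |
| Day | 28 days | 29 of 365 | 8% |
| Day | 31 days or more | 0 | 0% |
| Month and day | 14 days | 351 of 365 | 96% |
| Month and day | 183 days | 182 of 365 | 50% |

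These shares apply only to dates left partial after query. They are not shares of patients.

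**3. A negative record hidden in a positive total (constructed).** Dose D from 15 January to 14 March 2017 (59 days), then D/2 from 15 March, true stop 25 March (11 days), recorded as March 2017.

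| | True | Under 5.1.2 and 6.2 |
|---|---|---|
| Duration | 59 + 11 = 70 days | 59 − 13 = 46 days |
| Total dose | 59D + 5.5D = 64.5D | 59D − 6.5D = 52.5D |
| Average dose | 64.5D/70 = 0.92D | 52.5D/46 = **1.14D** |

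The average exceeds any dose taken, yet all three totals are positive. With a single dose record the days cancel and the average is unaffected unless the duration is zero.

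**4. Signature date.** A retrospective case starting on 1 June 2020 has a 183-day window ending 30 November 2020. Signed on 26 June 2022, the last collection date in Protocol 7.1, its duration is 730 + 25 + 1 = **756 days**, an excess of 573. One such case adds 573/N to the pooled mean: 5.7 days at an assumed N of 100, 0.57 at an assumed N of 1,000. A case starting 26 December 2021 and signed the same day gives 183 days, with no excess.

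The outer limit runs from the approval date (Protocol 5: "Xeljanz was approved by the Ministry of Food and Drug Safety (MFDS) on 02 April 2014") to 26 June 2022, which is 3,008 days. SAP 2.2.1 instead describes two years after re-examination, about 1 April 2022. That is 86 days earlier and gives 2,922 for the limit and 670 for the 1 June 2020 start. Both limits are corner cases.

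**The case against.** **A reader might infer that the signature-date rule gives wrong exposure.** The documents do not support that. SAP 4.2 lists treatment duration with no 6-month limit, and a patient who stayed on the drug until the signature did have that exposure. The rule also has a purpose: Protocol 7.3.2.1 measures joints at 3 months in PsA, so stopping at the evaluation date alone could cut exposure short. The CRF itself is not shown, study-duration text is redacted in both documents, and Protocol 9.2 extends safety reporting at least 28 days past the last administration. What stands is that, in the visible text, treatment after month 6 is assumed rather than recorded.

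**A reader might infer that the safety results are biased.** They are not, in the visible text. SAP 4.4 and 6.4 count events within 6 months of first dosing as patient incidence, with no person-time denominator. Efficacy does not use duration either.

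**Queries and range checks would catch the errors.** Queries should reduce partial dates, and a negative single-record duration would show as the minimum. But 5.1.2 exists for dates that stay partial, and the two-record example would pass a check on patient totals. The objection lowers the weight of the point without removing it.

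**Conclusion.** SAP 5.1.2 is wrong as written: combined with 6.2 it can return zero or negative days and milligrams, and an average dose above any dose taken. That follows from the date arithmetic and needs no assumption beyond a stop date that remains partial. How often this happens is unknown.

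The signature-date rule is a secondary point. Days beyond the 6-month window are unverified, and the excess can be large for late-signed retrospective cases, but the lag and the share of patients affected are not in the documents. No inflation of pooled exposure can be claimed, and a 6-month limit is a choice, justified by what is collected.

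Severity is minor, confined to descriptive treatment duration, total dose and, with several dose records or a zero duration, average dose.

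**What to change.** **SAP 5.1.2.** Require every imputed stop date to be no earlier than the start of its own dose record, and no later than the day before the next record starts or, for the last record, the end of the 6-month period. Where month and day are both missing and a later dose record exists, use the day before that record starts if treatment was continuous; otherwise report the duration as missing. Give the numbers of imputed and missing durations by completion status. The missing ones can include completers whose dose changed, so no direction of shift in the pooled mean should be assumed.

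**SAP 6.2.** Present duration, total dose and average dose for the 6-month period counted from first dose, and truncate ongoing records and recorded stop dates alike at its end. For treatment ongoing with 6 months completed (the CRF field beginning "If the patient completed 6 months treatment, check"), the stop date is the end of the period. For other ongoing records, use the last date on which treatment is documented, within the same bounds. Recorded exposure beyond the period may be listed separately. Do not use the signature date as a stop date.

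**Check.** Start 15 March 2017 with stop March 2017 becomes 1 day. The 1 June 2020 case, if it completed 6 months, becomes 183 days whatever the signature date.

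**Cost.** Two SAP rules and a few lines of programming. Reported exposure becomes shorter for some ongoing patients, and a few durations become missing. Day-01 imputation still shortens the remaining partial dates, by a mean of about 5 days at a true 7 days and about 15 days at 28 or more.
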